## 6.7. Sample Size Determination

The expected final sample size is between 25 and 50 subjects, depending on dropout rate and whether the study is prolonged by the inclusion of Part B. If for the final sample size  $\geq 80\%$  of

subjects exhibit < 4 mIU/mL suppression, efficacy will be claimed. It is actually expected that 85% to 90% response is likely. The table immediately below shows the lower one-sided 95% confidence limits for final sample sizes varying from 25 to 50 in increments of five subjects under the expectations of 85% suppression and 90% suppression.

Table 4 Numeric Results for One-Sided Lower-Limit Confidence Intervals for One Proportion Confidence Interval Formula: Simple Asymptotic with Continuity Correction

Confidence Level	Sample Size (N)	Actual	Proportion (P)	Lower Limit	Upper Limit
		Distance from P to Lower Limit			
0.950	25	0.137	0.850	0.713	1
0.950	25	0.119	0.900	0.781	1
0.950	30	0.124	0.850	0.726	1
0.950	30	0.107	0.900	0.793	1
0.950	35	0.114	0.850	0.736	1
0.950	35	0.098	0.900	0.802	1
0.950	40	0.105	0.850	0.745	1
0.950	40	0.091	0.900	0.809	1
0.950	45	0.099	0.850	0.751	1
0.950	45	0.085	0.900	0.815	1
0.950	50	0.093	0.850	0.757	1
0.950	50	0.080	0.900	0.820	1

In Table 4 the lower one sided confidence limit never falls below 70%. Suppression to < 4 mIU/mL in 70% of the subjects is considered to be clinically important by TOLMAR. Thus the sample size is thought to be adequate.

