9.1 Sample Size Determination

To determine the percentage of subjects with suppression of serum LH to < 4 mIU/mL following treatment with leuprolide acetate 45 mg, it is estimated that approximately 40 subjects would be sufficient for assessment of Part A and approximately 27 subjects for Part B, if invoked. Approximately 60 subjects may be enrolled in the study in order to get an appropriate number of assessable subjects.

The sample size was pragmatically determined based on the clinical trial size and response rate of other GnRH antagonists studies in CPP subjects.

The descriptive finding that will conclude efficacy is that ≥ 80% of subjects will exhibit < 4 mIU/mL LH suppression. This is conservative, since the dropout rate is unknown, and it is anticipated that the percent of subjects suppressed is likely to be at least 85%. Thus, 85% suppression or 90% suppression might be reasonably expected. However, the drop out in this

study could be slightly more than 50%, if Part B is invoked, thus depending on whether only Part A is carried out or Part B is invoked, the final available sample size after drop out could vary between 25 and 50 subjects given the planned recruitment of 60 subjects. Suppression to < 4 mIU/mL in approximately 70% of the subjects is considered to be clinically important if the full expectations of all drop-out are completed. Thus, the study is thought to have a sufficient number of subjects. If 85% of subjects enrolled are found to be suppressed we would expect a lower 95% one sided confidence interval under a fully realized drop out scenario (ie, 25 final subjects) of slightly more than 70%.

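### SAP Table 4's lower limits fall short of their labelled 95% confidence in 8 of 12 settings, and the 70% adequacy statement fails at its own worst case (N=25, 85% suppressed)

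*SAP*

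**What the plan says.** SAP 6.7 opens with the range it plans for: "The expected final sample size is between 25 and 50 subjects". Its Table 4 "shows the lower one-sided 95% confidence limits for final sample sizes varying from 25 to 50 in increments of five subjects". It does so for two assumed rates, 85% and 90%. The table title names the method: "Confidence Interval Formula: Simple Asymptotic with Continuity Correction". Every row carries a confidence level of 0.950, and the smallest printed limit is 0.713 (N=25, P=0.85).

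The section then reasons in three steps. First, "In Table 4 the lower one sided confidence limit never falls below 70" per cent. Second, suppression "in 70% of the subjects is considered to be clinically important by TOLMAR". Third, the sample size is therefore thought adequate.

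Protocol 9.1 makes the same argument at one point. If 85% are suppressed, it expects "a lower 95% one sided confidence interval under a fully realized drop out scenario (ie, 25 final subjects) of slightly more than 70" per cent, having called suppression in approximately 70% clinically important. It also says that the size was set pragmatically from the size and response rates of other studies in this condition. It gives about 27 subjects as sufficient for Part B.

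Efficacy is a separate matter. SAP 6.5 and 6.6 and Protocol 9.2 judge it by whether the observed percentage is at least 80%, with no confidence limit involved.

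**The concern.** A simple asymptotic limit for a proportion tends to sit too high when the proportion is near 0.85 to 0.90 and N is 25 to 50. The continuity correction only partly repairs this. A limit labelled 0.950 may then carry less confidence than it states.

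The margin over the 70% floor at N=25 is also thin (0.713), and 85% of 25 is 21.25 children, a count that cannot be observed. If the printed limit is too high by a few points at that row, the statement that 70% is cleared throughout the planned range is not supported where it matters most. That row is the worst case in the SAP and the one case that Protocol 9.1 describes.

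**Working it through.** **Inputs.** From SAP 6.7: N = 25, 30, 35, 40, 45, 50; P = 0.85 and 0.90; one-sided 95% (z = 1.645); continuity-corrected simple asymptotic formula; 70% floor. From Protocol 9.1: N=25 at 85%, and a Part B size of about 27.

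**Step 1. Reproduce the table.** L = P − z·√(P(1−P)/N) − 1/(2N).

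For N=25, P=0.85: 0.85 − 1.645 × √(0.1275/25) − 0.02 = 0.85 − 1.645 × 0.0714 − 0.02 = 0.7125, printed as 0.713. All 12 rows reproduce to three decimals. Without the correction the value would be 0.7325, so the named formula is the one used.

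**Step 2. Actual confidence.** For a true rate p, coverage is the binomial probability of the counts x whose limit L(x) is at or below p. At N=25, p=0.85, the formula gives 0.753 at 22/25 and 0.811 at 23/25, but 0.876 at 24/25 and 0.980 at 25/25. It therefore misses when x is 24 or 25. That probability is 0.0759 + 0.0172 = 0.0931, so coverage is 90.7%.

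**Step 3. Exact limit.** Clopper-Pearson one-sided lower limit: the 5% quantile of Beta(x, N−x+1), taken at x = N·P, which is fractional in some rows.

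| N | P | N·P | SAP limit | Coverage of SAP formula | Exact limit at N·P |
|---|---|---|---|---|---|
| 25 | 0.85 | 21.25 | 0.713 | 90.7% | 0.682 |
| 25 | 0.90 | 22.5 | 0.781 | 92.8% | 0.743 |
| 30 | 0.85 | 25.5 | 0.726 | 95.2% | 0.7005 |
| 30 | 0.90 | 27 | 0.793 | 95.8% | 0.761 |
| 35 | 0.85 | 29.75 | 0.736 | 91.3% | 0.714 |
| 35 | 0.90 | 31.5 | 0.802 | 87.8% | 0.775 |
| 40 | 0.85 | 34 | 0.745 | 95.1% | 0.725 |
| 40 | 0.90 | 36 | 0.809 | 92.0% | 0.786 |
| 45 | 0.85 | 38.25 | 0.751 | 92.2% | 0.734 |
| 45 | 0.90 | 40.5 | 0.815 | 94.8% | 0.794 |
| 50 | 0.85 | 42.5 | 0.757 | 95.4% | 0.741 |
| 50 | 0.90 | 45 | 0.820 | 88.8% | 0.801 |

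Coverage is below 95% in 8 of 12 settings. N·P is not whole in 8 of 12 rows. One row of 12 falls below 0.70 at its own proportion.

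**Step 4. Attainable counts at the critical sizes.**

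| Count | Observed | SAP formula | Wilson | Exact |
|---|---|---|---|---|
| 21/25 | 84.0% | 0.699 | 0.688 | 0.670 |
| 22/25 | 88.0% | 0.753 | 0.735 | 0.718 |
| 23/27 | 85.2% | 0.721 | 0.708 | 0.692 |

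At x = 21.25 of 25, taken literally, Wilson gives 0.699. The nearest whole count, 21/25, is below 70% by all three methods.

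**The case against.** **The sentence is true of the printed table.** That stands. Its minimum is 0.713, and there is no slip in the arithmetic. The fault lies in the interval method and in the conclusion drawn from it.

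**Planning tables are usually evaluated at an assumed proportion, and rounding up rescues every row.** This stands in part. Fractional counts are not an error in themselves, and 22/25 gives 0.718. But 22/25 is 88%, not the 85% that both documents assume, and at 85% taken literally the exact limit is still 0.682. At N=30 and N=35 the exact limit drops below 0.70 only if the count is rounded down (25/30 gives 0.681, 29/35 gives 0.689), so those sizes are not counted as failures.

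**Clopper-Pearson is conservative.** True: at N=25 its own coverage is 98.3% (true 85%) and 100% (true 90%). The shortfall at 23/27 depends on this choice, since Wilson gives 0.708. The shortfall at N=25 does not, although Wilson at 85% (0.699) misses only narrowly.

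**The floor is soft.** Protocol 9.1 says approximately 70%, and 0.68 to 0.69 is close to that. The SAP, however, states 70% flatly and claims that the limit never falls below it.

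Two stronger readings are tempting, and the documents do not support them. A reader might infer that these limits are the whole case for the sample size, but Protocol 9.1 also gives the pragmatic basis in other studies. A reader might also infer that the same formula will be used for the reported primary percentage. SAP Section 7 says only that intervals may be given in selected instances and names no method.

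**Conclusion.** The point holds at a limited size. Table 4's label of 0.950 is not met in 8 of 12 settings; the lowest coverage is 87.8%. Its limits are about 0.02 to 0.04 above the exact ones. The adequacy statement fails at N=25 with 85% suppressed, the worst case that both documents use: 0.682 exact against 0.713 printed, and 0.670 at 21/25. The other 11 rows stay at or above 70% at their stated proportions, N=30/85% only just (0.7005). At the Part B size of 27 the result depends on the method.

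This rests on a one-sided 95% level, independent subjects with a common suppression rate, and 70% read as a firm floor.

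A reader might go further and infer that the trial is too small or that the efficacy conclusion is at risk. The documents do not support that: no confidence limit enters the 80% rule or the decision to invoke Part B.

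**What to change.** 1. Recompute SAP Table 4 with exact (Clopper-Pearson) one-sided limits at attainable counts, showing the whole counts on either side of 85% and 90% where N·P is fractional. Add a row for N=27.
2. Restate the closing sentence of SAP 6.7 and the matching sentence in Protocol 9.1: the lower limit is about 0.67 to 0.68 for 25 subjects with about 85% suppressed, and about 0.69 at 23/27. Then say whether those values are still considered adequate against the 70% level, and align the SAP's 70% with the Protocol's approximate 70%.
3. State in SAP Section 7 that any confidence interval given for the primary percentage will use the exact method.

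The cost is one table and a few sentences. The stated limits become about 0.02 to 0.04 less favourable, and the method is somewhat conservative. No subjects are added, and the descriptive efficacy rule stays as it is.

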## 7. PLANNED STUDY ANALYSES

Statistical analyses for this study will be comprised of descriptive statistics presented over time or at predesignated time points of special interest. Baseline, efficacy, safety and PK endpoints will be evaluated using descriptive statistics. For example, comparisons between two time points will be carried out by contrasting descriptive outcomes that exist for each of those time points.

Descriptive evaluation will in general take one of four forms depending on the underlying metric of the variable under analysis.

- 1) If the metric is categorical the following information at minimum will be provided: count (numerator), base (denominator) and percentage (numerator/denominator) for each category and overall. For dichotomous categorical variables, confidence intervals may in

 Hintze, J. (2014). PASS 13. NCSS, LLC. Kaysville, Utah, USA. www.ncss.com.

selected instances be provided. The term used hereafter to denote this type of analysis will be *categorical descriptive analysis*.

2) If the metric is continuous or presumed continuous the following information at minimum will be provided: number of subjects, mean, standard deviation, coefficient of variation, minimum and maximum. Confidence intervals may in some instances be provided. The term used hereafter to denote this type of analysis will be *continuous descriptive analysis*.

3) Categorical variables compared across time may be presented as a shift table. For example, a laboratory test result could be normal, low abnormal or high abnormal. A shift table comparing values between baseline and end-of-study would show the number and percent of subjects with shift outcomes of the form normal to normal, normal to low abnormal, normal to high abnormal, high abnormal to normal, high abnormal to low abnormal, high abnormal to high abnormal, low abnormal to normal, low abnormal to low abnormal, and low abnormal to high abnormal. A simpler version of the table that omits direction of abnormality might be normal to normal, normal to abnormal, abnormal to normal, abnormal to abnormal. The term used hereafter to denote this type of analysis will be *shift table analysis*.

4) Serum concentrations will be analyzed by evaluating concentration at each time point using continuous descriptive analysis; and by evaluating the PK parameters AUC, Cmax and Tmax using continuous descriptive analysis. Since the PK sampling frequency in this trial is limited due to the age of the subjects, it will be expected that the PK parameters will have larger intra-patient variability. Concentration plots in the original and log scale will be created, combined over subjects and by subject. Continuous descriptive analysis will be provided for absolute values of AUC, Cmax and Tmax as well as log transformed values of these parameters. All together the above analyses in part or whole will be referred to as *PK analysis*.

Because this study collects data at many interim time points, extensive use of graphs to display categorical descriptive analysis results and continuous descriptive analysis results over time will be employed. This will facilitate an assessment of trend.

Further note that because tables containing categorical descriptive analysis and continuous descriptive analysis will exist for the various outcome parameters at each time point, selected time points of interest can be compared to each other for a specific purpose. For example, the medical writer can compare descriptive outcomes at visits after injection 2 to visits after injection 4 to evaluate GnRHa simulation results under a six and a five month injection separation schedule. Using specific comparisons of descriptive statistics at designated time points, objectives for the assessment of efficacy (see Protocol Section 9.2.2: Efficacy Evaluations) can be accommodated.

Plots of individual subject outcomes will be generated for all variable concentrations used in the PK/PD analyses (Leuprolide, LH, FSH, testosterone and estradiol concentration), bone age and height.

The table that follows summarizes the planned analyses for baseline, efficacy, safety and PK variables.

Table 5 Type of Analysis Applied to Baseline, Efficacy, Safety and PK Variables

Variable Class	Variable(s)	Analysis				Listed/Not Analyzed 	Time Points Analyzed (Visits) 
		Categorical Descriptive Analysis	Continuous Descriptive Analysis	Shift Table Analysis	PK Analysis		
Baseline	Presence of Informed Consent	x					Screening, Visit 7
Baseline	Inclusion/Exclusion Criteria	x					Screening
Baseline	Demographics (categorical)	x					Screening
Baseline	Demographics (continuous)		x				Screening
Baseline	Medical History (categorical)	x					Screening
Baseline	Medical History (descriptive)					x	Screening
Baseline	Meds/Treatments History					x	Screening
Baseline, Safety	Vital Signs		x				Screening, All Visits
Baseline, Safety	Weight		x				Screening, All Visits
Baseline, Efficacy	Height		x				Screening, All Visits
Baseline, Safety	Complete Physical Exam (categorical)	x					Screening, Visit 11
Baseline, Safety	Complete Physical Exam (descriptive)					x	Screening, Visit 11
Safety	Directed Physical Exam (categorical)	x					Visits 1, 2,3,5,6,7,8, 9 10
Safety	Directed Physical Exam (descriptive)					x	Visits 1, 2,3,5,6,7,8, 9 10

 All collected and derived variable values will be in listings. However, this column highlights information that is closely related to information found in an adjacent row of this table; will not be descriptively analyzed; but will be presented in a listing.

 This table assumes that Part B will be invoked. If Part B is not invoked visits will be altered to conform to the *Schedule of Assessments: Part A*.

Variable Class	Variable(s)	Analysis				Listed/Not Analyzed 	Time Points Analyzed (Visits) 
		Categorical Descriptive Analysis	Continuous Descriptive Analysis	Shift Table Analysis	PK Analysis		
Safety	Flare Symptoms	x	x 				Telephone interview weeks 26 & 46, Visits 2-11
Safety	Pregnancy Test	x					Visits 1, 5,7, 9, 11
Safety	Adverse Events	Reported in Listings and Summarized in Tabulations 					Throughout Study
Baseline, Safety	Laboratory Tests 	x	x	x			Screening, All Visits
Baseline	Hepatitis B/C Antibody	x		x			
Baseline, Safety	Serum Lipids (fasting)	x	x				Screening, Visits 1,7
Efficacy	Leuprolide, LH, FSH, Testosterone, Estradiol (basal)		x		x		Screening, All Visits
Efficacy	LH, FSH, Testosterone, Estradiol (GnRHa stimulation) 	x	x				Screening, All Visits
PK	Serum Leuprolide (basal)		x		x		Screening, All Visits
Efficacy	Tanner Staging  and Menses Presence or Change	x	x	x			Screening, Visits 3, 5, 7, 8, 9, 10, 11
Efficacy	All Exploratory Efficacy Endpoints 	x	x				Screening, All Visits

 See Appendix 3: Global Interview Symptom Assessment. Each item will be analyzed separately using categorical descriptive analysis. A count of total number of symptoms will be analyzed using continuous descriptive analysis.

 AEs will be coded using MedDRA which in turn will allow quantification of events. Number and percent of subjects reporting AEs will be tabulated for the Safety Population. Tabular summaries will be presented by System Organ Class (SOC) and Preferred Term (PT), and further by severity and relationship to the investigational product. In summaries of severity, subjects who reported more than one event that are mapped to the same SOC and/or PT will be counted only once under the strongest severity. In summaries of relationship, subjects who reported more than one event that are mapped to the same SOC and/or PT will be counted only once under each applicable relationship.

 Laboratory values include urinalysis, hematology and chemistry. Data are predominately continuous with a few categorical scales.

 For these variables a dichotomy will be evaluated (LH < 4 mIU/mL, FSH < 2.5 mIU/mL, estradiol < 20 pg/mL, testosterone < 30 ng/dL) using categorical descriptive analysis.

 Each five stage rating will be treated as a categorical scale and as a presumed continuous scale. Respectively, these will be analyzed using categorical descriptive analysis and continuous descriptive analysis. Categorical descriptive analysis will be applied to menses presence and menses change. Baseline to end-of-study stage shift tables for each Tanner category will be constructed.

 Exploratory efficacy endpoints are described in the Exploratory Efficacy Endpoint section. Some endpoints are categorical and others continuous, thus both categorical descriptive analysis and continuous descriptive analysis will be required.

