### **8.2.2. Secondary Efficacy Endpoints and Assessments**

Serving as secondary endpoints will be the following variables.

- The percentage of subjects with serum LH concentrations < 4 mIU/mL at 30 minutes following an abbreviated GnRHa Stimulation Test for any available measurement other than the measurement constituting the primary outcome variable (see above).
- The percent change from baseline in height at each available post-baseline measurement. Percent change is defined as  $((\text{change from Baseline})/(\text{Baseline})) \times 100$ .
- The growth velocity of height in cm/year at each available post-baseline measurement. Growth velocity is defined for each visit as  $(\text{change from Baseline})/[(\text{number of weeks since Baseline})/52]$ .
- The ratio of bone age at each given measurement point to chronological age at the same measurement points.
- Baseline to end-of-study stage shifts for each Tanner category.
- The percent change from baseline in hormonal concentration (LH, FSH, Testosterone, and Estradiol) at each available post-baseline measurement. Percent change is defined as  $((\text{change from baseline})/(\text{baseline})) \times 100$ .
- The percent change from baseline in systemic leuprolide concentration at each available post-baseline measurement. Percent change is defined as  $((\text{change from baseline})/(\text{baseline})) \times 100$ .

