## 9. SAFETY ASSESSMENTS

Selected endpoints described under “Baseline and Related information” also will serve as safety parameters. These endpoints are included in the list below.

- Vital Signs
- Weight
- Physical Examination
- Clinical Laboratory Assessments
- Pregnancy Test
- Adverse Events
- Serious Adverse Events

Categorical descriptive analysis, continuous descriptive analysis and shift table analysis will be applied to safety endpoints as described in Section 7: Planned Study Analyses.

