#### **14.5. Clinical Laboratory Evaluations**

In addition to categorical and continuous descriptive analyses as noted earlier, scatter plots of the baseline value (x-axis) and end of study (y-axis) will be completed for each clinical laboratory parameter. Reference ranges will be highlighted on the plots to identify laboratory assessments that are out of range.

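### Weight is a named safety endpoint, but the planned per-visit kilogram summaries cannot separate expected growth from excess gain; adding standardised scores and within-child change is a cheap improvement

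*SAP*

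**What the plan says.** Weight is measured in kilograms at every visit (Protocol 8.4.6; SAP 8.1.5), and no derived weight variable is defined. SAP 9 includes weight in its list of safety parameters and states: "Categorical descriptive analysis, continuous descriptive analysis and shift table analysis will be applied to safety endpoints". It refers to SAP 7 for which analysis applies to which endpoint.

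In SAP 7, the Weight row of Table 5 has a single mark, under continuous descriptive analysis, with the time points "Screening, All Visits". For that analysis "the following information at minimum will be provided: number of subjects, mean, standard deviation, coefficient of variation, minimum and maximum". SAP 7 gives, as an example of its descriptive approach, that "comparisons between two time points will be carried out by contrasting descriptive outcomes that exist for each of those time points".

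The protocol sets the same general style. Its synopsis says that safety analysis is descriptive only, that continuous data are summarised by n, mean, SD, minimum and maximum, and that all data are listed by subject. Protocol 9.2.1 treats weight as a demographic variable with descriptive statistics. Protocol 9.2.6 plans per-time-point summaries for vital signs and does not mention weight.

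**The concern.** Girls enter at 2 to 8 years and boys at 2 to 9, and they are followed to Week 48 (Part A) or Week 80 (Part B). Over that time a child's weight rises with normal growth. In a single-arm study no concurrent group shows how much rise to expect. A table of mean kilograms by visit therefore goes up whether or not gain is excessive, and it does not show how the individual changes are distributed.

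At stake is one part of the safety objective (Protocol 7.2; SAP 5.2). The report will contain a weight table that supports no group-level statement on weight as a safety outcome, and a reader who wants one must derive it from listings. Under SAP 4, an analysis outside the final SAP and its Appendix 4 is labelled post hoc.

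**Working it through.** The documents state no figure for weight, so there is none to reproduce. The check has three steps.

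**1. What is specified for weight, set beside other variables**

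| Variable | Table 5 analysis | Specified elsewhere |
|---|---|---|
| Weight | Continuous descriptive | No change, BMI or standardised score |
| Vital signs | Continuous descriptive | Per-time-point summary (Protocol 9.2.6) |
| Height | Continuous descriptive | Percent change, velocity, individual plots |
| Urinalysis, hematology, chemistry | Categorical, continuous, shift table | Baseline-versus-end scatter plots for clinical laboratory parameters |

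For height, SAP 8.2.2 adds "The percent change from baseline in height at each available post-baseline measurement" and "The growth velocity of height in cm/year at each available post-baseline measurement". The individual-subject plots in SAP 7 cover "Leuprolide, LH, FSH, testosterone and estradiol concentration), bone age and height", so weight is not among them. For laboratory data, SAP 14.5 adds that "scatter plots of the baseline value (x-axis) and end of study (y-axis) will be completed for each clinical laboratory parameter". The Table 5 mark alone does not show the gap, because height carries the same mark. The gap is that nothing elsewhere adds a change or a standardised score for weight.

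**2. What two visit summaries can and cannot give**

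Let s0 and st be the visit SDs and r the within-child correlation. The SD of the within-child change is sqrt(s0² + st² − 2·r·s0·st). The planned table gives s0 and st but not r. With equal SDs (s0 = st = s) the expression becomes s·sqrt(2(1 − r)). For an assumed r of 0.80 to 0.98:

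- r = 0.80: s·sqrt(0.40) = 0.632·s
- r = 0.98: s·sqrt(0.04) = 0.200·s

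The same two rows of the table thus fit a spread of individual change anywhere from 0.20 to 0.63 visit SDs. The equal SDs and the range of r are assumptions, not figures from the documents.

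A lesser point is that SAP 12 includes at each time point only subjects with data there, so the children behind two visit means can differ. SAP 12.3 partly softens this for early-termination safety data. Its size cannot be set from the documents.

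**3. How far mean weight rises with growth alone (illustration)**

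Expected rise = rate × time. The rate of 2 to 4 kg/year is an assumption. The times come from the protocol's schedules, which label each visit in weeks and in approximate months.

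| Last visit | Time | Rise at 2 kg/year | Rise at 4 kg/year |
|---|---|---|---|
| Part A, Week 48 | 48/52 = 0.92 year | 1.85 kg | 3.69 kg |
| Part A, Month 12 | 12/12 = 1.00 year | 2.0 kg | 4.0 kg |
| Part B, Week 80 | 80/52 = 1.54 years | 3.08 kg | 6.15 kg |
| Part B, Month 21 | 21/12 = 1.75 years | 3.5 kg | 7.0 kg |

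Across both labels, the rise by the last Part B visit is 3.1 to 7.0 kg with no excess gain. A child who stays on the same weight centile has a change in weight SD score near zero. Within-child change in kilograms would settle step 2 but would still contain this growth, so the standardised score is the essential addition.

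**The case against.** The strongest reply is that the plan never gives the weight table the task of detecting excess gain. Weight gain is not in the objectives, the background risks or the symptom checklist. Weight is handled like vital signs, its nearest peer in Table 5, under a uniform descriptive rule that the protocol synopsis also sets. The listed statistics are minimums (SAP 7 and 18.2), the sentence on contrasting time points is only an example, graphs over time are planned, and the mock tables in Appendix 5 are still to come. Listings, adverse event reporting and DSMB review at least quarterly remain.

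Much of this stands, and it limits the point. It does not remove it:

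- SAP 9 itself names weight as a safety endpoint, so its summary should be able to say something about safety.
- The trend graphs would show the same per-visit results.
- The further summaries named in SAP 18.2, such as median and quartiles, describe the same variable. None is a change or a standardised score.
- A suitable mock table may still appear, but nothing commits to one.

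A reader might infer that the SAP contradicts itself by giving height more than weight. It does not: height serves a stated objective, and it is not standardised for age or sex either. A reader might also infer that weight safety goes unmonitored, or that the drug is suspected of causing excess gain. The remaining safeguards answer the first, and the documents do not raise the second.

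A further fair criticism concerns the remedy. Every child must have bone age advanced by at least 1 year, and effective treatment may slow growth. Scores based on chronological age, weight SD score especially, can shift for those reasons alone.

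**Conclusion.** The point holds as a cheap improvement of the lowest severity. As specified, the weight summaries mix expected growth with any excess gain and leave the spread of within-child change undetermined, so they support no group-level statement on weight as a safety outcome. This follows from the text together with the age range and the single arm. It does not depend on the assumed inputs.

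The size is illustrative only. The 3.1 to 7.0 kg rests on the assumed 2 to 4 kg/year and on the two labels for the last Part B visit. The 0.20 to 0.63 visit SDs rest on the assumed correlation and equal SDs. A reader might turn the latter into a claim of lost precision, but the SAP plans no interval for weight change, so there is no planned precision to lose. No efficacy conclusion or decision rule is affected.

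**What to change.** In SAP 9 and Table 5:

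- Keep the kilogram summary by visit.
- Add weight and BMI SD scores for age and sex from one named growth reference.
- Take the Visit 1 predose value as baseline.
- Summarise within-child change from baseline at each visit: n, mean, SD, median, minimum and maximum, with a 95% interval as an option.
- State that the result is descriptive, that one reference serves several countries, and that advanced bone age and treatment-related slowing of growth can shift scores based on chronological age (weight SD score especially), so a change is not attributed to the drug.

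The cost is SAP wording and derived variables. No new measurement is needed: height and weight are scheduled together at the clinic visits (Protocol Tables 1 and 3), and sex and date of birth are collected (Protocol 8.4.2). If logged in Appendix 4 before the statistician examines the data, the addition counts as a priori under SAP 4. Version 1.4 recorded the addition of height velocity in the same change log. The main downside is having to choose a single reference for a multinational study.
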